4.2 Exclusion Criteria

Exclusion criteria are: 1) meet criteria for past or present psychotic or bipolar disorders; 2) inability to understand English well enough to complete questionnaires or participate in therapy; 3) pain due to malignant conditions, rheumatoid arthritis, frequent migraines or tension headaches, complex regional pain syndrome, or fibromyalgia syndrome; 4) lumbar surgery within past 6 mos; 5) pregnant; 6) signs of nerve root compression (i.e., positive straight-leg raise $<45^\circ$); 7) have liver disease such as hepatitis or cirrhosis; 8) have osteoporosis; 9) have an active suicidal ideation with intent; 10) opioid-dependency or daily use of Kratom; 11) inability to hold breath for 15 seconds; 12) acute trauma to spine; 13) long term use of corticosteroids; 14) have a spinal cord stimulator, an IT pump, or a similar device; 15) history of spinal fusion surgery; 16) arthritis of the hand, carpal tunnel syndrome, or any neuropathic pain diagnoses affecting the upper limbs; or 17) a BMI of ≥ 40 .

4.3 Study Enrollment Procedures

Participants will be recruited through referrals from staff at the University Pain Center, Midwest Orthopedic Clinic and Neurosurgery Clinic at Rush University, the Vanderbilt University Medical Center Interventional Pain Clinic, and the Osher Center for Integrative Medicine at Vanderbilt. Additionally, we will recruit in the community via flyers posted at community physician waiting rooms and other public sites, local newspaper ads, Facebook ads, and online patient recruitment systems (Vanderbilt e-mail recruitment system, My Research at Vanderbilt, Research Match). My Research at Vanderbilt is an informatics-based recruitment tool that uses Vanderbilt University Medical Center EMR data to match individuals expressing interest in research participation with studies which may be of interest to them. Research Match (ResearchMatch.org) is a national electronic, web-based recruitment tool that was created through the Clinical & Translational Science Awards Consortium in 2009 and is maintained at Vanderbilt University as an IRB-approved data repository. We have used all of these recruitment approaches in our prior work with a high degree of success. In addition, potentially qualifying individuals who

have participated in past studies in our labs who have expressed an interest in writing to be contacted for future research may be contacted as well.

Interested individuals will be able to contact the designated study research assistant by phone or email. Individuals expressing an interest will first be provided verbally with information on the study procedures, risks, and benefits, and if interested, will be given the opportunity to read the IRB-approved informed consent form. All questions from potential subjects will be answered by the study representative as accurately as possible. All individuals agreeing to participate will provide written informed consent prior to beginning any study procedures. Subject recruitment and consent procedures will be carried out by individuals designated and trained by each site PI and the IRB to carry out these procedures (i.e., the proposed research assistants). Potential subjects will be told that they will be compensated \$605 for their time and effort to participate in all of the assessment and therapy sessions. In the Consent Form, it will be emphasized that subjects may discontinue participating at any time and still receive prorated compensation. The recruiter will inform potential subjects that participation is completely voluntary, and they may withdraw at any time without penalty or running the risk of jeopardizing current and future treatment at the Rush or Vanderbilt medical centers.

Study patients (n=286) will be randomized to receive either MT or SMT. The order of drug administration for each laboratory session will also be separately randomized and counterbalanced (placebo vs. naloxone) for both of the assessment time points (in double-blinded fashion). All randomization will be carried out using the Proc Plan procedure in SAS version 9.2 (SAS Institute, Cary, NC). This SAS procedure will be used to generate a randomization schedule for each sequential study slot (MT vs. SMT and the order of naloxone/placebo administration in each set of lab visits). Study subjects will be assigned to these previously randomized study slots in the order that they are enrolled, and the previously determined randomization status associated with each slot will determine the intervention condition each subject is in and the order of drug administration for each session. This randomized order will be maintained even if study appointments are missed (applies only to drug order in laboratory sessions). In the event of a true study dropout, that slot is considered used and future subjects will not be assigned to that slot.

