A heat pain task using a Medoc TSAII NeuroSensory Analyzer (Medoc US., Minneapolis, MN) will then follow. This equipment will be used to assess heat pain threshold and tolerance using an ascending method of limits protocol as used in our prior work (68,71,72). The equipment to be used has a hardware temperature cutoff of 51°C in order to prevent tissue injury. Four trials each will be conducted for heat pain threshold and tolerance, with each trial conducted sequentially at 1 of 4 different non-overlapping sites on the non-dominant ventral forearm. An interval of 30 secs between successive stimuli will be employed. For threshold trials, the probe will start at an adaptation temp of 32°C, with the temp increasing at a ramp rate of 0.5°C/sec until the subject indicates that the stimulus has begun to feel "painful." For tolerance trials, the probe will start at an adaptation temperature of 40°C, with the temperature increasing at a ramp rate of 0.5°C/sec until the subject indicates maximum tolerance has been reached. Means of the 4 thermal pain threshold and tolerance trials will be derived for use in analyses. Immediately upon completion of the final heat pain tolerance trial, subjects will be asked to rate the overall pain experienced during this

trial using the MPQ. EO function will be operationalized as in our past work as changes in evoked pain responses between the placebo and naloxone conditions (68,71,72), with blockade effects on the visual analog scale (VAS) pain intensity measure of the MPQ considered primary.

Conditioned Pain Modulation (CPM)

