Efficiency of descending inhibition of pain (i.e., CPM) will be assessed using a protocol adapted from Gehling et al. (81) which found that combining heat pain (test stimulus) with cold pressor pain (conditioning stimulus) demonstrated acceptable test-retest reliability over a 3 day test-retest interval. CPM is a centrally-mediated effect (107), and therefore is expected to be observed at sites throughout the body, e.g., CPM elicited with stimuli applied to the back vs. the forearm is similar (102). As is common in the CPM literature, and to avoid any local sensitization confounds with stimuli applied to the back in CLBP patients, the current project will apply both the test and conditioning stimuli in the periphery. A cold pressor task [circulating ice water bath; see our prior work (112,113)] applied to the nondominant upper extremity will be the tonic conditioning stimulus, and the same TSA-II heat pain stimulus used in thermal pain testing (applied to the dominant forearm) will be the test stimulus. At the beginning of lab session 1, we will determine the heat pain stimulus temperature corresponding with an intensity rating of 60/100 for that individual. This will be done using a series of brief (5 sec) thermal stimuli applied starting at 44°C, based on our prior work indicating a mean thermal pain threshold and tolerance of 44°C and 48°C respectively in chronic back pain patients. This stimulus intensity will be increased/decreased incrementally by 0.5°C until the targeted perceived pain intensity of 60/100 is reached. This temperature (referred to hereafter as P60) will be used as the stimulus intensity for the test stimulus in all CPM procedures. These CPM procedures will entail: (a) Three assessments of heat pain ratings (once every 10 sec) in response to 30 secs of a constant thermal stimulus applied at the predetermined P60 target temperature to the dominant arm (“Pre-Conditioning Phase”), (b) Initiation of the tonic cold pressor conditioning stimulus to the nondominant hand (immersion in an ice water bath) and after 30 sec of exposure to the conditioning stimulus, (c) Three assessments of heat pain ratings (once every 10 sec) in response to 30 secs of the P60 thermal test stimulus applied simultaneously with the conditioning stimulus (“Conditioning Phase”; the total cold pressor duration will be 60 seconds). Change in mean thermal stimulus pain ratings during the pre-conditioning minus conditioning phases will be used to index CPM.

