6.2.6 Missed Evaluations

There is a 6-week window from baseline (visit 1) to the first lab session (visit 2). The first lab session (visit 2) must occur within this window and the second lab session (visit 3) must be within 2 weeks of the first. The first treatment visit (visit 4) is to

occur within one week from lab session 2 (visit 3).

If a participant misses an intervention session (MT or SMT) the staff will attempt to reschedule the visit for the following week, and the treatment schedule will be adjusted accordingly.

Treatment sessions 1-4 (visits 4-7) must all occur within 2 months of lab session 2 (visit 3). The first post-treatment lab session (visit 12) should occur within one month from treatment session 8 (visit 11).

The second post treatment lab session (visit 13) must occur within 2 weeks of the first post treatment lab session (visit 12).

The date of the follow-up assessments will be calculated from the date of the final post treatment lab session (visit 13). Participants will have a 2-week window around this date to complete the 3- and 6-month follow-ups (visits 14 & 15). Failure to complete these assessments within this window will result in the follow-ups being skipped.

All visits that fall outside of these allowable windows will be reported as protocol deviations.

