9.5.1 Primary Outcome

Our primary mechanism outcome is pre- to post treatment changes in EO function.

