9.6 Data Analyses

Primary analyses will be conducted on an ITT basis.

Aim 1: To determine the degree to which MT and SMT produce effects in nonspecific mechanisms.

The primary analyses will employ the two-sample t-test to compare mean change in each nonspecific mechanism within a noninferiority test construct to compare mean change in outcome from pre to post treatment between the two treatment arms. An overall, 2-sided, significance level of 0.05 will be used. Linear mixed models will be used as a supplemental analysis, allowing us to utilize all data collected, account for within subject variation, and model changes over time. The fixed effect part of the model will be

$Mechanism_{ij} = \beta_0 + \beta_1 Time_{ij} + \beta_2 Tx_i + \beta_3 (Tx_i * Time_{ij}) + \varepsilon_{ij}$ for subject i at visit j.

If β_3 is significantly negative ($p < .05$), this would indicate that the mechanism variable decreased more in SMT than in MT (Fitzmaurice, Laird, & Ware, 2011). In case of a significant interaction, we will test simple slopes of Time for each Treatment Condition separately AND by testing post treatment differences between MT and SMT controlling for pre-treatment values.

Candidate covariance structures will be assessed using the data's correlation structure and Akaike's Information Criterion (AIC). Random coefficients (e.g. random intercept and/or random slope) will be included in the model if they significantly improve the model fit as determined by the likelihood ratio test. Standardized residuals and Cook's distance will be used to assess the influence of outliers and individual observations. Residual plots will be used to check the multivariate normal distribution assumption. The pattern of missing data will be examined to determine its missing mechanism and the amount. If data are missing not at random (MNAR), data imputations may be used. If other deviations from the model assumptions are detected, appropriate measures will be taken to prevent inferential bias, e.g. data transformations and use of bootstrap techniques to compute standard errors.

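### The primary analysis of change in EO function leaves out the two randomised drug orders, so any first-to-second session shift stays in the result as avoidable noise

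*Protocol*

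**What the plan says.** Section 6.2.2 defines the measure: "EO function will be operationalized as in our past work as changes in evoked pain responses between the placebo and naloxone conditions", with the pain-intensity VAS of the McGill questionnaire as the primary response. One EO value therefore needs two sessions, one per drug condition. For the pre-treatment pair, section 6.2.6 says "the second lab session (visit 3) must be within 2 weeks of the first", and the post-treatment pair has the same two-week limit.

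Section 4.3 randomises the order. The schedule covers "the order of naloxone/placebo administration in each set of lab visits", and the order "will also be separately randomized and counterbalanced (placebo vs. naloxone) for both of the assessment time points".

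Section 9.5.1 sets the endpoint: "Our primary mechanism outcome is pre- to post treatment changes in EO function". Section 9.6, Aim 1, sets the test: "The primary analyses will employ the two-sample t-test to compare mean change in each nonspecific mechanism within a noninferiority test construct". The mixed model is supplemental and has fixed effects for time, treatment and their interaction. Its candidate covariates are site, age and baseline variables that differ between arms at p < .20. Drug order and session number appear in no analysis in section 9.6.

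**The concern.** Each EO value is a two-period crossover within a person. Participants repeat the same ischaemic and heat tasks within two weeks, so a shift between the first and second session (novelty, habituation, sensitisation) is possible. Such a shift adds to the naloxone-minus-placebo difference when placebo comes first and subtracts from it when naloxone comes first.

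If a person kept the same order before and after treatment, equal shifts would cancel in the change score. With the orders drawn separately they do not cancel for everyone, and an analysis without order terms carries the remainder as unexplained variance.

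The primary hypothesis is equivalence, planned at 0.851 power for the narrowest tabulated limits. Extra variance widens the interval that must fall inside those limits and makes an inconclusive result more likely. This is not simply detail left to an analysis plan, because the protocol itself fixes the primary test and the covariate list.

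**Working it through.** **Inputs.** From section 9.2: 120 per arm, SD 7.5, equivalence limits ±3.0, true difference 0, two one-sided tests at 5%. The session shift d (second minus first session, in the units of the SD and the limits) is an assumption, because the protocol gives none. I show d = 1, 2 and 3.

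**Step 1: reproduce the plan's figure.** Two one-sided t-tests with 238 df, integrated over the distribution of the sample SD, give 0.8515, 0.9500 and 0.9867 for limits of ±3.0, ±3.5 and ±4.0. The plan states 0.851, 0.950 and 0.987. The table is arithmetically right.

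**Step 2: how the shift enters.** Let o = +1 for placebo first and −1 for naloxone first.

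- Observed EO = true EO + o × d.
- EO change contains o_post × d_post − o_pre × d_pre.
- With independent orders, the added variance is d_pre² + d_post²: d² if only one pair shifts, 2d² if both shift equally.
- The expected contribution is the same in both arms, so the expected arm difference does not move.

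**Step 3: if 7.5 excludes order noise.** Unadjusted SD = √(56.25 + d²) or √(56.25 + 2d²). No order balance within arm is assumed.

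| d | One pair shifts: SD | Power | Both pairs shift: SD | Power |
|---|---|---|---|---|
| 0 | 7.50 | 0.851 | 7.50 | 0.851 |
| 1 | 7.57 | 0.844 | 7.63 | 0.836 |
| 2 | 7.76 | 0.820 | 8.02 | 0.787 |
| 3 | 8.08 | 0.779 | 8.62 | 0.704 |

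The variance increase for both pairs is 2d²/56.25: 3.6%, 14% and 32%. If the four order combinations are balanced within each arm and both pairs shift, simulation (20,000 trials per setting) gives unadjusted power of 0.815 at d = 2 and 0.767 at d = 3. Balance takes the shift out of the true error of the arm difference, but the t-test still counts it in its estimated SD. A model with arm and the two order indicators kept power at about 0.85 in every setting, and the mean arm difference was about 0 throughout.

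**Step 4: if 7.5 already includes order noise.** The stated 0.851 stands. Adjusted SD = √(56.25 − d²) or √(56.25 − 2d²), with 236 df.

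| d | One pair: SD | Power | Both pairs: SD | Power |
|---|---|---|---|---|
| 1 | 7.43 | 0.859 | 7.37 | 0.867 |
| 2 | 7.23 | 0.881 | 6.95 | 0.909 |
| 3 | 6.87 | 0.916 | 6.18 | 0.964 |

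**The case against.** The strongest reply is that no harm is demonstrated. The protocol reports no session shift, and at d = 0 the loss is nil. Counterbalancing already protects the arm comparison, the t-test is valid, and in an equivalence test extra variance costs power without inflating false claims of equivalence. The origin of the 7.5 is not stated; if it came from similar counterbalanced sessions, the planned power already allows for this noise. All of that stands. It limits the point to precision but does not remove it, because under either reading of the SD adjustment helps whenever d is not zero.

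Three stronger readings may tempt a reader, and the protocol does not support them.

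- **The trial is underpowered.** The lowest figure, 0.704, needs d = 3 in both pairs, no order balance within arm and an SD of 7.5 free of order noise, all at once. The protocol establishes none of these.
- **The sessions differ by design because of the heat calibration.** Section 6.2.2 does say "At the beginning of lab session 1, we will determine the heat pain stimulus temperature corresponding with an intensity rating of 60/100". That step belongs to conditioned pain modulation and is described only for lab session 1. Nothing shows that it shifts the primary EO measure, so the point should not rest on it.
- **Dropout could unbalance the orders and move the estimate.** Take 143 per arm, balanced by order, falling to 120. A 66/54 split in one arm means losing 5.5 from one order and 17.5 from the other, with the reverse in the other arm. Under random dropout that is about 3.8 standard deviations out. Chance imbalance without balance at entry is the same noise already counted in step 3, not an extra bias.

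It could also be said that an order indicator counts as a baseline variable. Even so, it would be considered only if it differed between arms at p < .20, and only for model-based analyses. The primary t-test would be unchanged.

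**Conclusion.** The point holds as a loss of precision. The protocol randomises two drug orders that can affect every EO value, then names a primary test and a covariate list that include neither. The stated 0.851 is reproduced and is not shown to be wrong.

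For d up to 3 points, the cost of not adjusting ranges from nothing to a fall in power to 0.704, with intermediate cases around 0.77 to 0.84. If the SD already contains the noise, the cost is a forgone gain, up to 0.964 at d = 3. These sizes depend on the assumed d, on whether one or both pairs shift, on order balance within arm (which section 4.3 does not specify) and on what the 7.5 contains. The direction does not depend on them: for any nonzero shift, adjusting for order is the more precise analysis.

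**What to change.** In section 9.6, Aim 1, estimate the arm difference in EO change, with its 90% CI, from a linear model containing arm and two indicators: drug order in the pre-treatment pair and drug order in the post-treatment pair. Compare that interval with the equivalence limits. Carry the same orders into the supplemental mixed model as fixed terms rather than LASSO candidates, with the order effect allowed to differ between the two time points. In section 9.2, state whether the 7.5 was obtained before or after removing order effects.

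The cost is a sentence or two of text, settled before the data are unblinded. The orders are already on the randomisation schedule, no data are added, and two of about 238 degrees of freedom are used. If there is no session shift, power stays at 0.851 to three decimals.

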5. STUDY INTERVENTIONS

5.1 Interventions, Administration, and Duration

Drug Manipulation

Although not actually an intervention, we will administer naloxone during half of the pain induction sessions in order to quantify endogenous opioid (EO) function. We will use a placebo-controlled opioid blockade procedure to assess treatment-induced changes in EO function, by comparing pain responses under placebo to pain responses after opioid blockade with naloxone at pre- and post-treatment. Naloxone is an opioid antagonist with a brief half-life (1.1 hours; 78). We will use a weight-

adjusted dose of 0.11 mg/kg with a maximum dose of 8mg (8mg dose for a 160 lb. individual, consistent with our past work 69-71). As in our past studies, naloxone in 20 ml normal saline will be infused over a 10-minute period through an intravenous cannula placed in the non-dominant arm. At this dosage, naloxone provides effective blockade of all three major opioid receptor subtypes (79). Naloxone is FDA approved, and appears to have no clinical effects in non-opiate dependent individuals. Thus, participants using opioid analgesics on a daily basis or within 3 days of each laboratory session (confirmed via urine drug screen) and/or experiences withdrawal symptoms with the initial naloxone administration, will be excluded. It has been used safely at similar dosages in previous studies, including our studies in CLBP samples (68-72). Peak naloxone activity will be achieved approximately 10 minutes following completion of the infusion. A second dose of naloxone (0.055 mg/kg with a maximum dose of 4mg; 4mg for a 160 lb. individual) will be infused following the thermal and ischemic tasks (before CPM procedures). This dose will be used to maintain adequate opioid blockade across the duration of pain-induction procedures.

Study Interventions

Both study treatment interventions will consist of 8 weekly, 1-1.5 hr individual sessions. For MT and SMT, the content of each session will be based on a standardized treatment manual. Manuals will contain detailed session by session information, instructions and scripts for therapists, and patient handouts.

Mindfulness Training (MT)

Patients will receive training in mindfulness through (a) body scan meditation, a gradual moving of attention through the body, accompanied by awareness of breathing and other bodily sensations while in a lying position, (b) sitting meditation, focusing on awareness of breathing, bodily sensations, thoughts, and emotions, practiced sitting on a chair or cushion, (c) gentle movement exercises intended to develop awareness (mindfulness) during movement. Each session includes practice of these mindfulness techniques. In-session didactic material, interactions and discussion on subjects' experiences of developing and applying mindfulness in everyday life are also part of each session. In-session activities include suggestions for application of mindfulness as a method for responding positively to stress; dealing with the challenges of pain; and exercises focusing on the challenges and achievements patients experience in integrating mindfulness into their lives and the stressful situations they encounter. Additional discussion will focus on stress reactivity. To help patients deal with obstacles to increasing mindfulness, they will be taught problem-solving skills to develop solutions to meet MT goals. Finally, patients will develop a written maintenance plan that includes a list of short- and long-term goals for applying mindfulness methods and a plan for dealing with possible setbacks.

Spinal Manipulation Therapy (SMT)

SMT sessions will reflect a similar visit pattern and duration as MT sessions. Recent

work showed small differences lacking clinical meaningfulness when comparing SMT provided 1, 2, or 3 times per week. (88) Furthermore, our visit pattern is consistent with professional guidelines (89,90). Thus, we believe our design is optimal in matching time required for MT sessions and also meeting effective SMT practice patterns. We will administer 2 SMT techniques each session, both of which have demonstrated effectiveness and are common for conservative management of individuals with CLBP. (37,38,91) See Appendix for description and illustrations. We will use scripted interactions between the physical therapist (PT) providing the SMT and subjects to stimulate therapist/subject relationships more consistent with the relationships that will develop in MT. Each SMT session will be organized as follows: 1) Participants will lie on the SMT table for 20 mins, while the PT sits approximately 6 ft away. As part of the script, the PT will review with subjects the inclusion/exclusion criteria ostensibly to ensure that nothing has changed. 2) The PT will perform the 2 SMT techniques during the next 20 mins. 3) Subjects will lie on the SMT table for the remaining 20 mins, while the PT sits approximately 6 feet away. As part of the script, the PT will ask subjects to perform a posterior pelvic tilt exercise. Subjects attempting to enter into discussion of issues beyond the scripted plan will be told, “I’m sorry but because this is a research study I am not allowed to discuss this with you.”

Each individual participant will be in the study for approximately 38 weeks. This includes a baseline assessment, 2 pre-treatment laboratory assessments, 8 therapy sessions, 2 post-treatment assessments, and 3- and 6-month follow-up visits.

Therapist Training, Adherence, Participant Engagement

Therapist training. Therapists for MT will be post-doctoral level clinical psychologists or other licensed healthcare providers (e.g., nurse practitioner) with prior experience delivering MT for chronic pain. Therapists for SMT will be licensed PTs. Therapists at Rush and Vanderbilt sites will receive training prior to conducting treatment sessions with study subjects. Initial training will consist of a 2-day didactic and experiential course conducted by [name] and [name] for MT and [name] for SMT. Therapists will be provided detailed manuals and outlines of treatment protocols, and the treatment strategies will be taught via direct instruction, recorded illustrations of techniques, and role-play of common scenarios. All instruction sessions will be digitally videotaped for reference and/or education of new therapists. Therapists will be certified to deliver each treatment by having supervisors (i.e., Drs. [name], [name] and [name]) rate tapes of practice role-play sessions prior to their working with study subjects. Mastery of each protocol will be required for therapists to deliver treatment in the research protocol.

Procedures to ensure consistency of treatment. To ensure that the therapists consistently follow the appropriate treatment protocol, four steps will be taken: (a) use of a detailed treatment manual; (b) weekly supervision sessions; (c) audio or video recording of sessions for treatment adherence ratings (see below), with these recordings and feedback from the adherence raters reviewed during the weekly supervision meetings conducted by [name], [name] and [name]; and (d) provision

of therapist feedback on treatment consistency and further didactics and role plays to correct “drift” if needed.

Treatment adherence, and therapist competence. Adherence refers to the extent to which a therapist uses interventions prescribed by a protocol. Ratings of adherence to the treatments will be conducted by [name], [name], [name] and an RA. Protocol adherence criteria will be developed for each session with satisfactory adherence defined as 90% or more of the maximum possible score on the adherence rating scale. Ratings of therapists' competence in delivering the interventions will be used to evaluate 20% of the sessions for each of the treatment conditions. Sessions to be evaluated will be randomly selected.

Participant engagement in treatment. Receipt of the intervention by the participant, as well as participant perceived difficulty in understanding session content, will be assessed via weekly patient engagement checklists after each session. Under supervision of [name] and [name], site RAs will evaluate the checklists for consistency.

